4.1 STUDY RATIONALE

Since the approval of anti-VEGF therapies, many countries and regions have set up retinal registries, observational studies, and databases containing information on patients with retinal diseases (Daïen et al., 2019). However, data captured within these different data sources are not always consistent and complete with respect to collecting information on the overall management of the patients treated with anti-VEGFs in retinal indications. The FaReal study therefore aims to fill the existing knowledge gaps by collecting long-term data on patients treated with faricimab, in order to:

- Evaluate the real-world evidence of faricimab (functional and anatomic effectiveness, durability, and safety) in nAMD and DME in a multi-country, regional setting.
- Describe the treatment patterns and explore the association between treatment patterns and effectiveness of faricimab.
- Evaluate the impact of treatment patterns on change in VA over time.
- Evaluate health economic aspects of previous anti-VEGF treatments and current treatment with faricimab.

The insights gathered in this study may help to further advance personalized healthcare initiatives in ophthalmology and allow a broader real-world evidence collection within EU countries, in a standardized data collection format.

5 RESEARCH QUESTION AND OBJECTIVES

5.1 RESEARCH QUESTION

The FaReal study aims to evaluate the effectiveness, safety, clinical insights and treatment patterns in patients treated with faricimab, in nAMD or DME (in at least one eye), in real-world routine clinical practice over a 2-year patient follow-up period. Additionally, the FaReal study also aims to describe and evaluate health economic aspects of previous anti-VEGF treatments and current treatment with faricimab.

5.2 OBJECTIVES

5.2.1 Primary and Secondary Objectives

Primary Objective	Primary Analysis
To evaluate the functional effectiveness of faricimab in nAMD and DME on visual acuity (VA) at 12 months in the real-world setting.	
 Change in VA (approximate Early Treatment Diabetic Retinopathy Study (ETDRS) letter score - see Appendix 3) from index date* to month 12.

Secondary Objectives	Secondary Analyses
To evaluate the functional effectiveness of faricimab in nAMD and DME on VA at specified intervals during the conduct of the study in the real-world setting.	
 Change in VA (approximate ETDRS letter score - see Appendix 3) from index date* to months 3, 6 and 24.
To evaluate the anatomical effectiveness of faricimab in nAMD and DME on central subfield thickness (CST) reduction	
 Change in CST (defined as the CST measured by the used OCT) from index date* to months 3, 6, 12 and 24 months (as measured per local standard clinical practice).

Secondary Objectives	Secondary Analyses
To describe retinal treatment patterns throughout study period	
 ● Number and percentage of eyes in each treatment regimen (i.e., Fixed regimen, T&E, PRN, Other - see Appendix 5) at 3, 6, 12 and 24 months of observation. ● Number of intravitreal injections per eye per year per indication overall (at month 12 and 24). ● Number of intravitreal injections in loading phase** for treatment naïve and anti-VEGF pre-treated patients (per pre-treatment type) ● Total number of visits, number of visits with or without treatment (observational) at 3, 6, 12 and 24 months of observation ● Number and percentage of eyes with treatment switch from faricimab, including reason for switch, at 3, 6, 12 and 24 months of observation for treatment naïve and pre-treated patients (per pre-treatment type).
To describe durability of faricimab treatment within different patient groups (indication, treatment naïve/pre-treated)	
 ● Number and percentage of eyes obtaining treatment intervals of Q8W, Q12W, Q16W and other at 12 months and 24 months of observation for treatment naïve and pre-treated patients (per pre-treatment type).
To evaluate the correlation/association between retinal treatment characteristics (durability and treatment patterns) and change in VA over time in nAMD and DME	
 ● Change in VA (approximate ETDRS letter score - see Appendix 3) from index date* to months 3, 6, 12 and 24, in relation to: 
 ○ Treatment regimen (Fixed, T&E, PRN, Other - see Appendix 5) ○ Number of intravitreal treatments ○ Total number of visits ○ Treatment intervals ○ Type of pre-treatment and number of previous injections for preceding regimen at index date ○ Length of diagnosis of disease at index date

CST = central subfield thickness, DME = diabetic macular edema, ETDRS = Early Treatment Diabetic Retinopathy Study, nAMD = neovascular age-related macular degeneration, PRN = pro re nata, T&E = Treat-and-Extend, VA = visual acuity, VEGF = vascular endothelial growth factor

*Index date is defined as the date of first faricimab treatment on eye-level. If both eyes are treated with faricimab and the treatment start dates are different, each start date will be used as index date for the respective eye.

**Loading phase is defined as per local label (for nAMD and DME)

5.2.2 Safety Objective

Safety Objective	Safety Analysis
To evaluate the ocular and systemic safety and tolerability for faricimab in nAMD and DME in the real-world setting.	
 Incidence, severity, duration, and outcomes of ocular and non-ocular adverse events.

DME = diabetic macular edema, nAMD = neovascular age-related macular degeneration

5.2.3 Exploratory Objectives

Exploratory Objectives	Exploratory Analyses
To evaluate changes over time in presence/absence of retinal fluid, as determined by imaging assessments according to investigator evaluation as per routine clinical practice, in relation to the number of treatments, treatment regimen, and investigator-determined disease activity	
 Presence/absence of fluid in relation to the number of treatments including loading dose, treatment regimen, and investigator-determined disease activity: 
 Proportion of eyes with presence/absence of intraretinal fluid (IRF) over time (index date*, months 3, 6, 12, 24) Proportion of eyes with presence/absence of subretinal fluid (SRF) over time (index date*, months 3, 6, 12, 24) Proportion of eyes with presence/absence of IRF and SRF over time (index date*, months 3, 6, 12, 24) Proportion of eyes with absence/presence of either IRF, SRF or both from index date* over time (index date, months 3, 6, 12, 24) Proportion of eyes with absence/presence of serous pigment epithelial detachment (PED) from index date* over time and change in height of PED if measured (index date*, months 3, 6, 12, 24)
To describe changes in VA over time in relation to presence/absence of fluid or PED	
 Change in VA (approximate ETDRS letter score - see Appendix 3) from index date* to months 3, 6, 12 and 24 for eyes in each fluid group at index date (no fluid present, presence of IRF, presence of SRF, presence of serous PED, presence of both IRF & SRF)
To describe distribution of patients according to change in VA in nAMD and DME in the real-world setting.	
 Number and proportion of eyes, over time (from index date* to months 3, 6, 12 and 24), with approximate ETDRS letter score¹ of:

Exploratory Objectives	Exploratory Analyses
	
 ○ 70 or more (20/40 Snellen equivalent). ○ 36 to 69 (between 20/40 and 20/200 Snellen equivalent). ○ 35 or less (20/200 Snellen equivalent). ● Proportion of eyes gaining ≥ 15, ≥ 10, ≥ 5, or >0 letters in VA¹ from index date* over time. ● Proportion of eyes losing ≥ 15, ≥ 10, ≥ 5, or >0 letters in VA¹ from index date* over time.

To evaluate changes over time in presence/absence of anatomical features
	
nAMD specific endpoints: Number and percentage of eyes with the following, at index date* and months 3, 6, 12, 24:
 
 ● presence/absence of atrophy² ● presence/absence of fibrosis³ ● presence/absence of serous PED⁴ (also adding height of PED if measured) ● presence/absence of hemorrhage⁵ 
DME specific endpoints: Number and percentage of eyes with the following, at index date* and months 3, 6, 12, 24:
 
 ● presence/absence of epiretinal membrane (ERM)⁶

To evaluate the health economic perspective and specific treatment patterns of anti-VEGF treatment in nAMD and DME
	
For eyes pre-treated with any anti-VEGF:
 
 ● Type of anti-VEGF treatments received before index date* ● Time spent on each pre-treatment ● Number of previous injections for previous treatment ● Treatment interval of the last preceding treatment before entering the study. 
For all eyes (both naïve and pre-treated) the below will be described following the index date:
 
 ● Number and percentage of eyes in each treatment regimen (i.e., Fixed regimen, T&E, PRN, Other - see Appendix 5). ● Number of injections per eye per year per indication. ● Total number of visits, number of visits with or without treatment (observational), and time intervals between treatments, per year.

DME = Diabetic macular edema, ERM = Epiretinal Membrane, ETDRS = Early Treatment Diabetic Retinopathy Study, IRF = intraretinal fluid, nAMD = neovascular age-related macular degeneration, OCT= optical coherence tomography, PED = pigment epithelial detachment, PRN = pro re nata, RPE= retinal pigment epithelium, SRF = subretinal fluid, T&E = Treat-and-Extend, VA = visual acuity, VEGF = vascular endothelial growth factor

*Index date is defined as the date of first faricimab treatment on eye-level. If both eyes are treated with faricimab and the treatment start dates are different, each start date will be used as index date for the respective eye.

¹ Approximate ETDRS letter score conversion table can be found in [Appendix 3](#)

² Atrophy definition: Defined as cRORA (Complete loss of photoreceptors and the retinal pigment epithelium (RPE) in the central 3 mm), atrophy is to be assessed as per the treating physician (Sadda S et al 2018, Guymer RH et al 2020, Savastano MC et al 2020).

³ Fibrosis: Hyperreflective material below the neurosensory retina on OCT (may have a multilaminar appearance) accompanied by different amounts of RPE destruction & photoreceptor loss. It is to be evaluated by the treating physician in the central 3 mm (Willoughby AS et al 2015, Gräfe MGO et al 2020).

⁴ Serous PED: Separation between the RPE and the inner most aspect of Bruch's membrane. Is to be evaluated in the central 3 mm.

⁵ Hemorrhage to be evaluated by the treating physician in the central 3mm

⁶ ERM: to be evaluated by the treating physician in the central 3 mm

6 RESEARCH METHODS

6.1 STUDY DESIGN

6.1.1 Overview of Study Design

The FaReal study is a non-interventional, prospective, multinational, multicenter study designed to collect real-world data on patients treated with faricimab in nAMD and DME in the real-world routine clinical practice with primary prospective data collection (NIS PDC) and retrospective collection of prior medical/treatment history data from medical records.

Participation in this study will not change or influence a patient's standard of care in any way. The decision to start treatment with faricimab must be taken independently by the treating physician and before the decision to invite the patient into the study.

This study aims to enroll approximately 850 patients from approximately 65 sites (in 18 countries in region Europe and Israel). The expected duration of the study is approximately 4 years.

Adult patients fulfilling the eligibility criteria who sign informed consent (as required per local regulations) will be enrolled and followed up prospectively from enrollment until completion of 2 years of participation, death, withdrawal of consent, participation in an investigational ophthalmology clinical trial, early termination of the study, or discontinuation of the study site, whichever occurs first. Patients are free to withdraw participation at any time.

Retrospective data will be collected for pre-treated patients pertaining to their previous anti-VEGF treatments.

All patient visits will be conducted according to usual local clinical practice. No study-specific visits are mandated by the study protocol, no patient visits or remote consultations are mandated by the study protocol, and no additional tests will be performed on patients due to their participation in this study. Data will be collected only when patients present for their routine visits or are contacted remotely. Retrospective data from enrolled patients will be collected from the patient's medical history.

Data recorded at each visit will be collected, including some data that may not be routinely recorded in patient medical records but is part of the clinical routine for a specific patient. Where applicable, analysis will be conducted at specific time points (e.g., 3, 6, 12 and 24 months from index date). The derivation of the analysis value per time point will be described in the Statistical Analysis Plan (SAP) and may use data from visits placed in the appropriate window around the timepoint of interest for analysis (e.g., ± 30 days, ± 60 days). Subgroup analyses, for example by region, country, baseline characteristics, or other factors, will be performed as defined in the SAP. Further details of the planned analyses are provided in [Section 6.7](#) and will be fully described in the SAP.

The study population is intended to reflect the real-world use of faricimab treatment; therefore, minimal inclusion and exclusion criteria will be used. The study population will comprise patients treated with faricimab, for nAMD (Cohort 1) or DME (Cohort 2). Cohorts 1 and 2 will each be further divided into 2 sub-cohorts: treatment naïve (first-line) sub-cohort and anti-VEGF pre-treated (second-line) sub-cohort. For further details please refer to [Section 6.7](#).

Approximately 40% of the patients in Cohort 1 and Cohort 2 (treatment naïve sub-cohorts) will be enrolled after the decision to initiate intravitreal faricimab treatment has been taken as part of routine clinical practice as first-line treatment. The remaining patients in Cohort 1 and 2 (pre-treated sub-cohorts) may already have received intravitreal anti-VEGF treatment previously.

After enrolment, patients in both cohorts will be prospectively followed up during the faricimab treatment period (estimated as approximately 2 years). Patients who discontinue faricimab treatment for this study or switch to another treatment will be followed up until completion of 2 years of participation, death, withdrawal of consent, participation in an investigational ophthalmology clinical trial, early termination of the study, or discontinuation of the study site, whichever occurs first.

Treatment after switch from faricimab in both cohorts will be according to standard of care and as deemed appropriate by the treating physicians.

Anonymized data will be shared with the medical and scientific community to foster research and support evidence generation. The data elements collected will address different types of research questions through registry-based studies such as secondary data use (SDU) studies.

Start Date of Study

Patient enrollment will be initiated at each site, upon approval from regulatory authorities and IRBs/ ECs, as per local regulation and site agreement implementation and approval of faricimab treatment in nAMD and/or DME according to local labeling. The study start date will be the date of the first patient enrolled.

Study Duration

The expected duration of the study is up to 4 years, depending on the enrollment period duration. This includes approximately 1 to 2 years of recruitment and 2 years for follow-up of every patient (unless the patient discontinues early from the study).

Faricimab—F. Hoffmann-La Roche Ltd

Protocol MR45586, Version 1.0

Baseline Date and Index Date

Baseline is defined as the date when a patient initiates treatment with faricimab in at least one eye (first eye in case of both eyes being treated).

Index date is defined as the date when treatment is initiated at the eye-level. If both eyes are treated with faricimab and the treatment start dates are different, each start date will be used as the index date for the respective eye.

Enrollment Date

Enrollment date is the date the patient signs the Informed Consent Form to participate in this study.

Enrollment date cannot occur earlier than index/baseline date.

End of Study

The study ends when all participants have either completed at least 2 years of follow-up or have ended their participation in the study due to death, withdrawal of consent, participation in an investigational ophthalmology clinical trial, early termination of the study, or discontinuation of the study site, whichever occurs first.

The end of the study date will be the date on which the last information pertaining to the last included patient is recorded in the database.

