6.2.1 Rationale for Patient Population

This study aims to collect data from a broad real-world patient population treated with faricimab in nAMD and DME, as per clinical practice and labeling under EMA label or Food and Drug Administration (FDA) label (Israel) authorization and as per country label requirement. Therefore, minimal eligibility criteria will be applied to ensure a broad population.

As the primary objective of this study is to evaluate the effectiveness of faricimab for nAMD and DME on VA at 12 months after treatment initiation in the real-world setting, eligibility criteria focus on those patients' eye(s) that are initiating treatment at the time of enrollment. It is acknowledged that the effectiveness of faricimab may be different depending on whether an eye was previously treated with anti-VEGFs. Treatment naïve eyes are of particular scientific and medical interest as effectiveness and safety

outcomes will not be hindered by any long-term effects of previous treatments. Furthermore, a prospective follow-up of patients will enable a better recording of safety data, which is an important objective of this study.

Treatment naïve patients and pre-treated patients will be recruited in this study. Patients who had previously received intravitreal anti-VEGF treatment will be enrolled to assess the effectiveness of faricimab in switch patients and to incorporate the health economic aspects of previous treatments. The number of participants with prior intravitreal anti-VEGF therapy will be limited to 60% as the maximum proportion of the total and each indication enrolled.

The rationale for capping the number of pre-treated participants is based on the heterogeneous nature of this population with potentially a history of long-standing disease and irreversible retinal damage that may limit the possibility of detecting additional VA improvements.

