Treatment and management (by eye) for health economic analysis perspectives (pre-treated and treatment naïve eyes), from index date until end of study	
 ● Treatment regimen (i.e., Fixed regimen, T&E, PRN, Other) ● Number of injections per eye per year per indication (nAMD, DME). ● Total number of visits, number of visits with or without treatment (observational), and time intervals between treatments, per year.
Treatment and management (by eye) during study period, from index date until end of study	
 ● Treatments received for the indications nAMD, DME (type of treatment: anti-VEGF injection, laser therapy, corticosteroid injections or steroid implants), with date of therapy. ● Therapy switch: (date and reason)

Category	Variable
	
 ● Treatment discontinuation/termination (date and reason) ● Details of other procedures that could potentially elevate/deteriorate visual acuity (VA) ● Treatment regimen (Fixed regimen, T&E, PRN, Other) ● Number (dates) of injections ● Number of loading dose intravitreal injections (per eye) ● Number (dates) of visits with and without treatment (observational) ● Treatment intervals of Q8W, Q12W, Q16W and other ● CST over time (as measured per local standard clinical practice), by eye, (including method, software settings and type of OCT) ● Eyes with presence of IRF ● Eyes with presence of SRF ● Eyes with presence of serous PED, height of PED (if measured) ● Eyes with presence of atrophy^b ● Eyes with presence of fibrosis ● Eyes with presence of hemorrhage ● Eyes with presence of ERM
Concomitant medications (ocular and non-ocular), from index date until end of study	
 ● Ocular concomitant medications (type, indication and treatment time) ● Non-ocular concomitant medication (type, indication and treatment time)
Visual acuity (VA) by eye, from index date until end of study	
 ● VA (as measured per local clinical practice) including method of VA assessment - scale and type of correction (e.g., Best-corrected, Corrected, Pinhole, Uncorrected), and date of assessment.

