Imaging assessments (by eye) as per routine clinical practice (during visits for the retinal indications), from index date until end of study Note: Diagnostic images for this study will not be stored, hence assessment of images by investigators must be well-defined.	
 ● Optical coherence tomography (OCT)-imaging assessment type (e.g. SD-OCT, SS-OCT), machine used ● Results, including: 
 ○ SRF assessment (presence/absence) ○ IRF assessment (presence/absence) ○ CST assessment (numerically) ○ Serous PED assessment (presence/absence and height of PED if measured)
Safety events (all ocular and non-ocular AEs), from index date until end of study	
 ● Type of AE: 
 ○ AE/SAE ○ AESI ○ Ocular/non-ocular ● Onset date and resolution date ● Outcome ● Seriousness ● Severity ● Action taken ● Relationship to therapy (i.e., related or unrelated) ● For ocular events: eye(s) affected

AE = adverse event, AESI = adverse events of special interest, anti-VEGF = anti-vascular endothelial growth factor, CME = cystoid macular edema, CST = central subfield thickness, DME = diabetic macular edema, ERM = epiretinal membrane, HbA1c = Hemoglobin A1c, IRF = intraretinal fluid, IVT = intravitreal treatment,

MNV = macular neovascular membrane, nAMD = neovascular age-related macular degeneration, OCT = optical coherence tomography, PCV = polypoidal choroidal vasculopathy, PED = pigment epithelial detachment, PRN = pro re nata, RPE= retinal pigment epithelium, SAE = serious adverse event, SD-OCT = spectral domain optical coherence tomography, SRF = subretinal fluid, SS-OCT= swept-source optical coherence tomography, T&E = treat-and-extend, VA = visual acuity, YAG laser = yttrium aluminum garnet laser

^a To be assessed as per the treating physician.

^b Atrophy definition: Defined as cRORA (complete loss of photoreceptors and the RPE) in the central 3 mm), atrophy is to be assessed as per the treating physician (Sadda S et al 2018, Guymer RH et al 2020, Savastano MC et al 2020).

^c Serous PED: Separation between the RPE and the inner most aspect of Bruch's membrane. Is to be evaluated in the central 3 mm.

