6.3.1 Visual Acuity

The primary effectiveness variable is VA. VA will be collected at index date and at all available follow-up measurements. Information on the scale and type of correction (e.g., Best-corrected, Corrected, Pinhole, Uncorrected) during assessment, and the date of assessment, will be collected for each VA assessment, as available per routine clinical practice. If possible, and within routine clinical practice, it is recommended that the patient is assessed in the same manner across visits.

VA will be collected as measured per local practice and will then be converted automatically in the eCRF to the approximate ETDRS letter score ([Gregori et al., 2010](#)). Details of the conversion to approximate ETDRS letter score are outlined in [Appendix 3](#).

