6.7.2 Effectiveness Analyses

6.7.2.1 Primary Effectiveness Analyses

Primary effectiveness analyses will be performed per cohort and per sub-cohort, at the eye-level, for the EFAS-EL.

The primary effectiveness endpoint is the change in VA (approximate ETDRS letter score) from index date to month 12 per nAMD and DME and per treatment naïve and pre-treated sub-cohorts. VA will be measured as per the local practice at index date and at month 12. To allow statistical analysis of the different clinical methods used to measure VA, the assessments will be automatically converted to the approximate ETDRS letter score. The approximate ETDRS letter score conversion table can be found in [Appendix 3](#).

Both actual values at index date and month 12 and change from index date in VA (approximate ETDRS letter score) to month 12 will be summarized descriptively.

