6.7.6 Determination of Sample Size

No formal sample size calculation linked to hypothesis testing has been done for this descriptive study. Sample sizes will be calculated for each of the treatment naïve and pre-treated sub-cohorts of cohort 1 (nAMD) and cohort 2 (DME).

For the primary endpoint change from baseline in VA to month 12, we calculate the precision of the 95% CIs for the mean change in VA given the sample size anticipated to be enrolled by the sites, and assuming a range of standard deviations (SD) that was reported in the literature (Kern et al., 2021; Kiss et al., 2020; Holz et al., 2020a; Mitchell et al., 2018; Mitchell et al., 2020; Lotery et al., 2017) for treatment naïve patients, and assuming a 5% drop-out rate. Precision is defined as the width of the confidence interval of the mean change in VA from 0 to 12 months. We anticipate that the SD will be equal or lower for pre-treated patients, as their VA might have stabilized by the time they enroll into the study. The estimated number of patients per cohort/sub-cohort is presented in Table 3.

Table 3: Sample Size for the Primary Effectiveness Variable - Change in VA at 12 months

Cohort & Sub-cohort	Sample Size	Precision at SD=12	Precision at SD=14
Treatment naïve patients in nAMD	240	3	3.6
Pre-treated patients in nAMD	360	2.5	3
Treatment naïve patients in DME	100	5	5.6
Pre-treated patients in DME	150	4	4.6

DME = diabetic macular edema, nAMD = neovascular age-related macular degeneration, SD = Standard Deviation, VA = visual acuity

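### Pre-treated eyes are measured from the switch day with no earlier VA or CST on record, so any rebound from a poor reading at the switch cannot be told apart from a faricimab effect

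*Protocol*

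**What the plan says.** Section 6.7.2.1 of the protocol sets the origin of the primary endpoint: "The primary effectiveness endpoint is the change in VA (approximate ETDRS letter score) from index date to month 12", reported per indication and per sub-cohort. Section 6.7.2.2 gives CST change the same origin. Section 6.1.1 fixes the date: "Index date is defined as the date when treatment is initiated at the eye-level". In a pre-treated eye that is the day of the switch.

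Collection of the outcome starts on that day. Section 6.3.1 states "VA will be collected at index date and at all available follow-up measurements". Table 1 (section 6.3) heads the VA row "Visual acuity (VA) by eye, from index date until end of study" and gives imaging, which includes CST, the same period.

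The look-back covers therapy only: "Retrospective data will be collected for pre-treated patients pertaining to their previous anti-VEGF treatments". Table 1 lists the type of earlier anti-VEGF drug, date of first treatment, time on each drug, number of injections and last interval. In Appendix 2 the retrospective column is marked only for prior treatment and management, not for VA or imaging. Table 1 does list a switch reason, but for switches during the study period, not for the switch to faricimab.

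Section 6.2.1 says why these patients are enrolled: "to assess the effectiveness of faricimab in switch patients". They are 510 of the 850 planned patients (360 nAMD, 150 DME; section 6.1.3). Section 6.9 does not mention regression to the mean.

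**The concern.** A reading that is unusually low for an eye tends to be followed by a higher one, even if nothing about the eye has changed. If part of the pre-treated group was switched because the latest VA or OCT looked worse, and that reading is the index value, some of the later gain in VA or fall in CST is recovery from a chance low (or high) point. A single-arm change score counts that recovery as effectiveness.

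The usual protection in a study without a comparator is the eye's own earlier course. Here it will not be in the database. This is not a matter the SAP can settle later, because no analysis can use values that were never recorded. It also arises in eyes with a perfectly good same-day index reading, so it is separate from any problem of missing baselines.

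At stake is the reading of the primary endpoint in the two pre-treated sub-cohorts. Section 6.2.1 itself expects that long-standing disease may limit further VA gains in these eyes, so an artefact of one or two letters would not be trivial beside the result.

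**Working it through.** **1. The plan's own precision figures.** Table 3 (section 6.7.6) gives the full width of the 95% interval, with 5% drop-out.

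Width = 2 × 1.96 × SD / √(0.95 × n)

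| Pre-treated | n | SD 12: computed (stated) | SD 14: computed (stated) | Half-widths |
|---|---|---|---|---|
| nAMD | 360 | 2.54 (2.5) | 2.97 (3) | 1.27 to 1.48 |
| DME | 150 | 3.94 (4) | 4.60 (4.6) | 1.97 to 2.30 |

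Table 3 reproduces and is not in dispute. It describes sampling error and says nothing about bias.

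**2. Illustration with no drug effect.** The documents give neither the within-eye variation of VA nor the reasons for switching, so every input here is an assumption:
- reading SD w = 4, 5 or 6 letters, independent between readings;
- the eye is truly stable;
- the switch follows a reading at least 5 letters below the mean of the previous three;
- that same reading is the index value;
- a share f = 10 to 30% of switches arises this way, and the rest carry no artefact.

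Let D be the mean of the previous three readings minus the trigger reading. Its SD is s = w × √(4/3). The covariance of the trigger reading with D is −w², so the expected rebound at a later reading is

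gain = (w²/s²) × s × λ = 0.75 × s × λ, with λ = φ(5/s) / [1 − Φ(5/s)].

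| w | s | λ | Gain per triggered eye | f = 10% | f = 20% | f = 30% |
|---|---|---|---|---|---|---|
| 4 | 4.62 | 1.592 | 5.5 | 0.55 | 1.10 | 1.65 |
| 5 | 5.77 | 1.419 | 6.1 | 0.61 | 1.23 | 1.84 |
| 6 | 6.93 | 1.307 | 6.8 | 0.68 | 1.36 | 2.04 |

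Simulation of the same model agrees. The sub-cohort mean is inflated by about 0.6 to 2.0 letters.

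**3. Against the half-widths.** In nAMD (1.27 to 1.48), a 10% share stays well inside, a 20% share is about level with the lower figure, and a 30% share exceeds both. In DME (1.97 to 2.30), only the extreme corner (2.04) passes the lower figure.

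**4. How far the result depends on the assumptions.** Same model, still with no drug effect:
- Index value taken at the visit after the trigger reading: apparent gain 0.0 letters. The rebound has happened before baseline.
- 25 to 50% of eyes have a real, persistent 8-letter decline: the apparent gain in triggered eyes falls from 5.5–6.8 to about 2.1–4.9 letters.
- No switch triggered by a reading (f = 0): the artefact is 0.

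**5. Testing a possible remedy.** Taking the mean of the index and three previous readings as baseline gives 0.0 letters in truly stable eyes. With the real declines of step 4 it gives a spurious change of about −2.9 to −5.0 letters in triggered eyes. It is therefore not a neutral correction.

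No figure is offered for CST, since the documents give nothing from which to build one. The direction would be an overstated reduction.

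**The case against.** The strongest objection is that the premise is not in the protocol. No section says why pre-treated eyes are moved to faricimab. Section 4 mentions extended dosing intervals as well as efficacy, and Table 1 records the last treatment interval. A switch made for the interval creates no artefact. Nor does the protocol say that the decision and the index reading fall on the same day. All of this stands, which is why the bias can only be called possible and its size unknown.

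A reader might infer that the primary endpoint in these sub-cohorts is biased upward as a matter of fact, or that a rebound of 5.5 to 6.8 letters is to be expected. The documents do not support either. That range applies only to triggered eyes that are truly stable and whose trigger reading is also the baseline.

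A reader might also take section 6.7.6 as assuming that these eyes are stable. It says only "as their VA might have stabilized by the time they enroll into the study", to justify an SD no larger than in naïve eyes. It is not a claim about the baseline value.

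It is also fair to say that the study is descriptive, reports pre-treated eyes separately, plans subgroups by index VA and pre-treatment type (section 6.7.4.4), and admits limited internal validity and no comparison with other manufacturers' products (section 6.9). These points temper what will be claimed. None of them reveals whether a rebound is present, and the stated aim in switch patients remains.

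**Conclusion.** The point holds in conditional form. The protocol measures VA and CST change in pre-treated eyes from the switch day, collects no earlier values and no reason for the switch to faricimab, and has no comparator. If some switches follow a poor reading that doubles as the index value, the change from index may overstate effectiveness, and the study will be unable to say by how much.

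Under the stated assumptions the VA inflation is about 0.6 to 2.0 letters. It can exceed the planned half-width in nAMD and lies mostly within it in DME. Under other equally admissible assumptions it is near zero. The case for change rests on this indeterminacy, not on a demonstrated bias: a few chart values would show whether the problem exists.

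**What to change.** - **Table 1 and the retrospective column of Appendix 2:** for pre-treated eyes, add dated VA and CST from the last two or three routine visits before the index date, where on file, and the reason for the switch to faricimab.
- **Analysis:** present the pre-index course beside the post-index course, and show change from index by reason for switch.
- **Averaged baseline:** use a baseline that averages earlier readings only as a labelled sensitivity analysis, stating that it biases change downward in eyes with real decline before the switch.
- **Section 6.9:** name regression to the mean as a limitation for pre-treated eyes.

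The cost is some retrospective data entry from records already opened for injection history. No visit or test is added, so the study stays non-interventional. Since patients may enroll up to 3 months after starting faricimab, some index values will in any case come from the chart. History will be incomplete for referred patients, and the number of eyes with earlier readings should be reported.
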